| Blood for Plasma MK-6482 and PT3317
Assay |     |             | Х | X  | Х     | X     | X     | X     |                    | To be collected at predose, and at 0.5, 1, 1.5, 2, 3, 4, 5, 6, 9, 12, 24, 36, 48, 72, 96, and 120 hours postdose.   |  |

MK-6482-020-02 FINAL PROTOCOL

| All Groups   |  |             |   |    |       |       |   |   |                    |   |  |
|--|--|-------------|---|----|-------|-------|---|---|--------------------|---|--|
|  |  |             |   | In | terve | ntior | 1 |   |                    | Notes   |  |
| Scheduled Day  | Scr  | -1
(C-I) | 1 | 2  | 3     | 4     | 5 | 6 | Poststudy
or ET | Poststudy (follow-up) will occur approximately 14 days after study intervention administration [Sec. 8.11.4]. |  |
| Blood for Protein Binding  | Blood for Protein Binding X To be collected at predose.  |             |   |    |       |       |   |   |                    | To be collected at predose.   |  |
| Pharmacodynamics   |  |             |   |    |       |       |   |   |                    |   |  |
| Blood for Erythropoietin   |  |             | Х | Х  | Х     | Х     | Х | Х | X                  | To be collected at predose, and at 24, 48, 72, 96, and 120 hours postdose and poststudy.                      |  |
| Biomarkers   |  |             |   |    |       |       |   |   |                    |   |  |
| Blood for Genetic Analysis   |  |             | Х |    |       |       |   |   |                    | To be collected predose from enrolled participants only [Sec. 8.8].   |  |
| Abbreviations: AE=adverse event, BMI=body  |  |             |   |    |       |       |   |   |                    |   |  |
| ECG=electrocardiogram, EM=extensive metal  | ECG=electrocardiogram, EM=extensive metabolizer, EPO=erythropoietin, ET=early termination, FSH=follicle-stimulating hormone, Hem=hematology, HIV=human |             |   |    |       |       |   |   |                    |   |  |
| immunodeficiency virus, HR=heart rate, IM=intermediate metabolizer, NCI-ODWG=National Cancer Institute - Organ Dysfunction Working Group, RR=respiratory rate, SAE=serious adverse event(s), Scr=screening, T=body temperature, UA=urinalysis, UGT=uridine 5'-diphospho-glucuronosyltransferase. |  |             |   |    |       |       |   |   |                    |   |  |

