## 2.2.2 Preclinical and Clinical Studies

### 2.2.2.1 Preclinical Pharmacokinetics and Metabolism

MK-6482 PK was evaluated in mice, rats, dogs, and monkeys. MK-6482 has low aqueous solubility and high permeability (BCS Class 2) and is well absorbed following oral administration in animals at clinically relevant doses. The oral bioavailability of MK-6482 was shown to be high in mice (approximately 100%), moderate in dogs and monkeys (33% and 53%, respectively), and low in rats (18%). The *in vitro* plasma protein binding of MK-6482 ranged from 45 to 61% across species (45% in human plasma).

Following an oral dose of [C]MK-6482 in rats, radioactivity distributed rapidly to most tissues and was reversible. The mean overall recovery of dose ranged from 93.9% to 97.1%. Biliary excretion accounted for 85% and 80.2% of the radioactive dose in bile-duct cannulated male and female rats, respectively.

*In vitro* and *in vivo* metabolism studies for MK-6482 revealed primarily oxidation and O glucuronidation biotransformation pathways. The oxidation biotransformation pathways were greatest in rats, and similar between humans and dogs. PT3317, the primary metabolite of MK-6482 found in dog and monkey plasma samples, was confirmed by chemical synthesis to be a glucuronide. UGT reaction phenotyping with recombinant UGTs was used

to determine that PT3317 formation is mediated by UGT2B17, which is mainly expressed in the small intestine. Importantly, PT3317 has no activity against HIF-2 $\alpha$ .

Urinary excretion was found to be a minor pathway for elimination of MK-6482 ( $\leq$ 4% of dose) and PT3317 ( $\leq$ 13% of dose) for rats, dogs and monkeys.

A summary of MK-6482 nonclinical PK and metabolism is contained in the IB supplied by the Sponsor. The IB should be reviewed in conjunction with this study protocol.

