Following enrollment of all participants with moderate hepatic impairment, the healthy matched control participants will be enrolled. Each healthy control participant will be matched to the mean age ( $\pm$  15 years) and mean BMI ( $\pm$ 20%), sex (similar males/female ratio in each group), and UGT2B17 genotype (at least 2 IMs and 2 EMs) of participants with moderate hepatic impairment. If a UGT2B17 PM moderate hepatic impairment participant is enrolled in the study, a UGT2B17 PM healthy matched control participant will be included. If after reasonable efforts, a UGT2B17 PM healthy matched control participant is not enrolled, an additional participant with moderate hepatic impairment participant), who is not UGT2B17 PM, will be enrolled. This additional moderate hepatic impairment participant should be matched to the mean age ( $\pm$  15 years) and BMI ( $\pm$  20%) of the other 8 hepatically impaired participants. The final healthy matched control participant (ie, the 8th healthy control participant), who is also not UGT2B17 PM, should also be matched to the mean age ( $\pm$  15 years), BMI ( $\pm$  20%), and sex (with a similar male/female ratio in each group) of the 8 moderate hepatic impairment participants (ie, not including the 9th hepatically impaired participant).

On Day 1, participants will receive a single oral dose of 80 mg MK-6482, followed by serial blood sampling collection up to 120 hours postdose to characterize the PK of MK-6482 and PT3317. Serial blood sampling will be collected up to poststudy for erythropoietin measurements. Safety will be monitored throughout the study.

Because this is a Phase 1 assessment of MK-6482 in humans, the PK, pharmacodynamic, and safety profiles of the compound are still being elucidated. This protocol is therefore written with flexibility to accommodate the inherent dynamic nature of Phase 1 clinical studies. Refer to Section 8.11.6 for examples of modifications permitted within the protocol parameters.

Specific procedures to be performed during the study, including prescribed times and associated visit windows, are outlined in Section 1.3 of the SoA. Details of each procedure are provided in Section 8.

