### 4.2 Scientific Rationale for Study Design

Available preclinical data indicate that MK-6482 is anticipated to be predominantly eliminated by hepatic metabolism, therefore hepatic impairment may affect the PK of MK-6482. The purpose of this study is to compare PK of MK-6482 in participants with moderate hepatic impairment to the PK in participants with normal hepatic function.

This study employs healthy control participants with normal hepatic function that will be reasonably matched to the mean demographic parameters of the moderate hepatic impairment group to control for the influence of covariates.

The sample size of approximately 8 participants enrolled in each group (moderate hepatic impairment and healthy control) has been selected following the FDA Guidance for Industry: Pharmacokinetics in Patients with Impaired Hepatic Function (FDA 2003). Additional participant(s) may be enrolled if a participant discontinues from the study before the completion of the PK assessment to ensure there are at least 8 evaluable participants in each group.

The Child-Pugh classification (Table 1) will be used to categorize hepatic impairment due to its widespread use and acceptance by regulatory agencies (including the US FDA [FDA 2003]). The general study design is aligned with the relevant FDA guidelines for drugs that undergo substantial hepatic metabolism. A survey by the FDA of several PK studies conducted in participants with varying degrees of hepatic impairment, where Child-Pugh scale was used to assess hepatic impairment, has demonstrated a correlation between oral drug clearance and degree of hepatic impairment. In the current study, participants with chronic, stable moderate hepatic insufficiency will be enrolled using the Child-Pugh scale. The scale employs five clinical measures of liver disease as listed in Table 1 and Table 2. Assessment of each clinical measure is scored on a scale of 1 to 3, with 3 indicating most severe derangement. A composite of all five scores for each clinical measure is determined for each participants with composite scores of 7 to 9 on this Child-Pugh scale are classified as having moderate hepatic impairment.

| Parameter  | 1 point    | 2 points   | 3 points   |
|--|------------|--|--|
| Serum albumin (g/dL)   | >3.5       | 2.8 to 3.5   | <2.8   |
| Total serum bilirubin (mg/dL)  | <2         | 2 to 3   | >3   |

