#### 8.6 Pharmacokinetics

Plasma samples for evaluation of MK-6482 and PT3317 PK will be collected at scheduled time points as delineated in the SoA.

The decision as to which plasma samples collected will be measured for evaluation of PK will be collaboratively determined by the Sponsor. If indicated, these samples may also be measured and/or pooled for assay in an exploratory manner for metabolites.

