## 9.1 Statistical Analysis Plan Summary

This section contains a brief summary of the statistical analyses for this study. Full detail is in the SAP to be provided separately.

Detailed methodology for summary and statistical analyses of the data collected in this study will be documented in an SAP. The SAP will be prepared by Celerion and agreed upon with the Sponsor. This document may modify the plans outlined in the protocol; however, any major modifications of the primary endpoints definition and/or its analysis will also be reflected in a protocol amendment. Additional statistical analyses other than those described in this section may be performed if deemed appropriate.

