## 9.4 Analysis Endpoints

The primary PK endpoints will be AUC0-inf and Cmax of MK-6482 following a single oral dose of MK-6482 to participants with moderate hepatic impairment compared to those in healthy matched control participants.

Additional PK endpoints will be other PK parameters of MK-6482 including AUC0-last, AUC0-24, AUC%extrap, C24, Tmax, apparent terminal t/2,  $\lambda z$ , CL/F and Vz/F. Relevant PK parameters for PT3317 will also be presented.

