# **10.8** Appendix 8: Blood Volume Table

| All Participants  | Prestudy         | Treatment
Period | Poststudy | Total
Collections | mL Per
Collection | Total mL/
Test |
|---|------------------|---------------------|-----------|----------------------|----------------------|-------------------|
| Safety Laboratory Safety Tests  |                  |                     |           |                      |                      |                   |
| (including hematology, serum
chemistry, FSH)   | 1                | 4                   | 1         | 6                    | 12.5                 | 75                |
| INR/PT  | 1                |                     | 1         | 2                    | 3.5                  | 7                 |
| Blood for Planned Genetic
Analysis   |                  | 1                   |           | 1                    | 8.5                  | 8.5               |
| Blood for MK-6482 and PT3317
PK  |                  | 17                  |           | 17                   | 4                    | 68                |
| Blood for Protein Binding   |                  | 1                   |           | 1                    | 4                    | 4                 |
| Blood for UGT2B17 Genotyping  | 1                |                     |           | 1                    | 3                    | 3                 |
| Blood for CYP2C19 Genotyping  | 1                |                     |           | 1                    | 3                    | 3                 |
| Blood for Serum Erythropoietin  |                  | 6                   | 1         | 7                    | 3.5/8.5 a            | 24.5/59.5         |
| Total Blood Volume per Particip  | ant b |                     |           |                      |                      | 193/228 mL        |
| a Blood for serum erythropoietin sa
b If additional PK/pharmacodynam | amples may l     |                     |           |                      |                      | may be            |

obtained.

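### Does the predose protein-binding sample need a stated endpoint and analysis before the exposure comparison can be relied on?

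*Combined protocol and SAP*

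**What the plan says.** The protein-binding sample appears in two places. Section 1.3 has the row "Blood for Protein Binding X To be collected at predose", in a table that covers all groups and directly after the plasma pharmacokinetic (PK) sampling row. Section 10.8 (Appendix 8) has a row "Blood for Protein Binding": one collection of 4 mL in the treatment period, for all participants.

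The only other mention of binding is background. Section 2.2.2.1 reports that in vitro "plasma protein binding of MK-6482 ranged from 45 to 61% across species (45% in human plasma").

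Section 8.6 covers the two analytes: "Plasma samples for evaluation of MK-6482 and PT3317 PK will be collected at scheduled time points as delineated in the SoA". Section 9.4 states that "The primary PK endpoints will be AUC0-inf and Cmax of MK-6482" and adds an open list of further parameters, none of them unbound. Section 9.6.2 models AUC0-inf, AUC0-24 and Cmax on the log scale and plans plots of PK against albumin, among other Child-Pugh laboratory components. Section 9.1 says of the analysis: "Full detail is in the SAP to be provided separately". It also allows additional analyses, and it asks for a protocol amendment only when the primary endpoints or their analysis undergo major change.

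**The concern.** Blood is taken from every participant for a named purpose, yet the objectives (Section 3), endpoint rationale (4.2.1.1), PK procedures (8.6), endpoints (9.4) and analysis (9.6) contain no binding assay, unbound fraction or unbound parameter. Section 4.1 says "On Day 1, participants will receive a single oral dose of 80 mg MK-6482", so a predose sample holds no study drug. The unbound fraction can then be measured only by adding drug to the plasma in the laboratory, a step that is not described.

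The stake is interpretation of the main result. The unbound GMR equals the measured GMR times the ratio of unbound fractions, impaired over control. Albumin is one of the five Child-Pugh measures, so reduced binding in the impaired group is conceivable. In that case the planned GMR would understate the rise in unbound exposure, and enrolling more participants would not remove the shift. The sample could answer the question but, with no stated use, might yield no result.

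**Working it through.** **Is the draw really planned?** The rows of Appendix 8 other than erythropoietin are 75 + 7 + 8.5 + 68 + 4 + 3 + 3 = 168.5 mL. Adding 24.5 or 59.5 mL for erythropoietin gives 193 or 228 mL, the stated totals. Without the 4 mL binding sample the totals would be 189 and 224 mL. The draw is planned.

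**The plan's precision figures (Section 9.10).** Half-width = 1.645 x SD x sqrt(2/8).
- AUC0-inf: 1.645 x 0.574 x 0.5 = 0.472, as stated.
- Cmax: 1.645 x 0.256 x 0.5 = 0.211, as stated.

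**Possible size of a binding effect.** The control unbound fraction is 1 - 0.45 = 0.55, from the in vitro figure. If the impaired group loses a fraction f of binding capacity, its unbound fraction is 0.55/(1 - 0.45f), so the multiplier on the GMR is 1/(1 - 0.45f). The values of f are assumptions; the documents give none.

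| Assumed f | Unbound fraction | Multiplier | Measured GMR of 1.50 becomes |
|---|---|---|---|
| 0 | 0.550 | 1.00 | 1.50 |
| 0.20 | 0.604 | 1.10 | 1.65 |
| 0.35 | 0.653 | 1.19 | 1.78 |

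If binding vanished altogether, the multiplier would be 1/0.55 = 1.82. That is a ceiling, not an expectation.

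**Against the planned precision.** The log multipliers are ln(1.099) = 0.094 and ln(1.187) = 0.171.
- AUC0-inf: 0.094/0.472 = 20% and 0.171/0.472 = 36% of the half-width.
- Cmax: 0.094/0.211 = 45% and 0.171/0.211 = 81%.

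**How firm is the assumed range?** A cross-check needs two more assumptions: that albumin is the binding protein, and that normal albumin is 4.0 to 4.5 g/dL. The two-point albumin band in Table 1 (2.8 to 3.5 g/dL) then gives f from 1 - 3.5/4.0 = 0.125 to 1 - 2.8/4.5 = 0.378, and multipliers of 1.06 to 1.20. This agrees with the range above but does not confirm it, because the documents do not name the binding protein.

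It also places every impaired participant in that band. Low albumin is not an entry requirement: a score of 7 to 9 can be reached through bilirubin, clotting, ascites and encephalopathy, and the only liver-test quota is on bilirubin. If half the impaired group had the assumed loss and half had none, the log shift would halve, to multipliers of exp(0.047) = 1.05 and exp(0.086) = 1.09.

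**What the plan delivers as written.** Group GMRs with 90% confidence intervals for plasma AUC0-inf, AUC0-24 and Cmax, plus plots of PK against albumin. None of these depends on the binding sample. No sample-size or precision figure would change if an unbound summary were added or left out.

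**The case for a change.** The best case for a change is that the protocol does state uses for comparable samples. Plasma PK has Section 8.6, erythropoietin has 8.7 and 9.7, and genetic blood has 8.8. Section 9 is also detailed enough to list the extrapolated AUC percentage and metabolite-to-parent ratios, so brevity does not fully explain the silence on binding. The albumin plots cannot supply an unbound ratio. In an open-label study, an analysis left unstated could be chosen after the data are seen. For Cmax, the assumed shift is a sizeable share of the planned half-width.

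The inconsistency in documentation stands; a sentence of purpose in Section 8.6 would be tidier. The rest carries less weight. The protocol gives no bioanalytical method for MK-6482, PT3317 or erythropoietin either, so an undescribed laboratory step is normal here. The primary endpoints and their model are fixed, so freedom over a supplementary binding summary does not extend to the main result. The Cmax share rests on the same unsourced loss of binding and looks large mainly because Cmax varies little.

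A modelled unbound GMR would need assumptions of its own: that binding does not depend on concentration and does not change after the predose draw. It would be an extra analysis and would not correct an error. It also cannot be shown that exposure will be compared only on total drug, because the separate SAP was not among the documents available.

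**Conclusion.** No change follows. This is a gap in documentation that analysts fill sensibly. The sample's label and its place in the PK part of the schedule show its purpose. A descriptive summary of the unbound fraction by group can go into the SAP under Section 9.1, and unbound AUC0-inf and Cmax can be added there as exploratory parameters if wanted. No wrong rule or figure is involved, and the planned primary comparison is valid without it.

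A loss of binding capacity of 20% to 35% throughout the impaired group would shift the GMR by a factor of 1.10 to 1.19; no loss gives 1.00. Those figures rest on the in vitro value of 45% bound and on an assumed loss for which the documents give no evidence. The conclusion would be open to revision only if the separate SAP or the Study Operations Manual, neither of which was available, showed that the sample is not to be assayed or serves another purpose. Even then the primary analysis would stand.

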## 2 INTRODUCTION

MK-6482 (belzutifan) is a potent oral small molecule inhibitor of HIF-2 $\alpha$ , that is indicated for the treatment of adult patients with VHL-RCC, CNS hemangioblastomas, or pancreatic neuroendocrine tumors not requiring immediate surgery. MK-6482 is also being evaluated as a treatment option for patients with solid tumor and patients with advanced RCC. HIF-2 $\alpha$  is a transcription factor that is overexpressed in many cancers and promotes tumorigenesis. HIF-2 $\alpha$  forms a heterodimeric complex with HIF-1 $\beta$  (also called ARNT), and subsequently binds to hypoxic response elements of target genes which regulate hypoxic signaling, tumor cell growth and survival. MK-6482 binds to HIF-2 $\alpha$ , preventing its heterodimerization with HIF-1 $\beta$ , and resulting in decreased transcription and expression of HIF-2 $\alpha$  target genes. The proposed therapeutic dose of MK-6482 is 120 mg once daily.

### 2.1 Study Rationale

The liver is involved in the clearance of many drugs through a variety of oxidative and conjugative metabolic pathways and/or through biliary excretion of the unchanged drug or metabolites. Alterations of excretion and metabolism by hepatic insufficiency can lead to lower drug clearance. Hepatic disease can alter the absorption and disposition of drugs as well as their efficacy and safety. In accordance with the FDA hepatic impairment guidance (FDA 2003), a Sponsor should evaluate the PK of its investigational drug in hepatic impaired participants when hepatic metabolism and/or excretion accounts for a substantial portion (>20% of the absorbed drug) of the elimination of the parent or active metabolite.

*In vitro*, MK-6482 is a substrate of UGT2B17, CYP2C19 and CYP3A4. UGT2B17 and CYP2C19 are polymorphic enzymes and the relative contribution of these 2 enzymes to the elimination of MK-6482 has been elucidated by multiple means including an exploratory pharmacogenetic analysis, a population PK analysis, and a clinical evaluation of the impact of specific UGT2B17 and CYP2C19 variants on the single-dose PK of MK-6482. The collective results of these analyses indicate that UGT2B17 is the major route of elimination in individuals who express this enzyme. MK-6482 glucuronide (PT3317), represents the major circulating human metabolite formed by UGT2B17. Accordingly, PT3317 exposures are greatly reduced in participants who have decreased or absent UGT2B17 activity. In individuals with absent UGT2B17 activity, CYP2C19 is a major route of elimination. The overall contribution of CYP3A4 to MK-6482 metabolism is anticipated to be minor in individuals with intact UGT2B17 and CYP2C19 enzyme activity. A human ADME study (MK-6482-008) is currently ongoing, and anticipated to confirm that hepatic metabolism represents a major elimination pathway (>20% of the absorbed drug) for MK-6482.

Since MK-6482 is anticipated to be predominantly eliminated by hepatic metabolism, evaluation of the impact of hepatic impairment on MK-6482 PK is useful. The primary objective of this study is to investigate the impact of moderate hepatic impairment on MK-6482 PK.

### 2.2 Background

Refer to the IB for detailed background information on MK-6482.

## 2.2.1 Pharmaceutical and Therapeutic Background

MK-6482 is a potent and selective inhibitor of HIF-2 $\alpha$  both *in vitro* and *in vivo*. HIF-2 $\alpha$  is known to form a heterodimeric complex with HIF-1 $\beta$ , which is also referred to as ARNT; the heterodimer can then bind to hypoxic response elements in target genes and induce their transcription. The PAS domains of HIF are essential for heterodimerization of the HIF-2 $\alpha$ :HIF-1 $\beta$  subunits, a prerequisite for target gene induction. A unique ligand-binding pocket has been identified in the PAS-B domain of HIF-2 $\alpha$  (Scheuermann et al., 2013). MK-6482 binds in this pocket, thereby disrupting HIF-2 $\alpha$ :ARNT heterodimerization and directly inhibiting the function of HIF-2 $\alpha$ .

In tumor cells in which HIF-2 $\alpha$  is activated, MK-6482 block the transcription of several genes involved in oncogenesis, including cyclin D1, VEGF-A, and the glucose transporter SLC2A1. MK-6482 has showed antitumor activity in mouse VHL-deficient tumor xenograft models with nearly complete regression of established tumors after oral administration of MK-6482 at 0.3 mg/kg bid. No activity was observed with MK-6482 treatment in VHL-proficient ccRCC tumors. MK-6482 showed no off-target activity against a panel of 76 receptors and 8 ion channels (at concentrations up to 12.5  $\mu$ M), and no off-target activity at 10  $\mu$ M against a panel of 40 protein kinases and 2 protein phosphatases.

